### **Trial steering and the data safety and monitoring committee**

An independent data monitoring committee (DMC) will be constituted prior to the conduct of the trial and this committee will continue to serve to oversee until the completion of the trial.

The DMC will convene on a periodic basis; normally, after data on the first 20% of participants have been enrolled into a study, and at the conclusion of enrollment. The committee will be advised on a regular basis of participant enrollment; receive (verbatim) each report of a serious adverse event (SAE), with an investigator assessment of causality/attributability of at least possibly related to study that is provided from the investigator and follow-up SAE reports will be promptly forwarded to the Chair.

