### **Adverse Event Reporting**

All adverse drug event (ADE) and serious adverse events (SAE) will be tracked in the participant's study file and REDCap and reported to Island Health's Clinical Research Ethics Board (CREB). As per Health Canada, a SAE is defined as "an adverse drug reaction that requires inpatient hospitalization or prolongation of existing hospitalization, that causes congenital malformation, that results in persistent or significant disability or incapacity, that is life threatening or that results in death". Each SAE that is attributed to FMT is subject to expedited reporting to Health Canada and should be reported individually in accordance with the data element(s) specified in the Health Canada/ICH Guidance Document E2A: "Clinical Safety Data Management: Definitions and Standards for Expedited Reporting". Expedited reports are required for events that meet all of these three criteria: serious, unexpected and a suspected causal relationship; this is defined as any untoward medical occurrence that at any dose results in

any one of the following: results in death; is life-threatening; requires inpatient hospitalization or prolongation of existing hospitalisation; results in persistent or significant disability/incapacity or is a congenital anomaly/birth defect. An event reaction causality scoring system will be used to determine the probability of the relationship of the event to study intervention. Source documents will be used to capture AEs and SAEs. All AEs will be reported to the CREB within 24 hours of the PI being aware of the event.

Known side effects of FMT are described in table 6.0; these potential effects are listed in the informed consent and participants are advised to report these and any other effects that they feel is relevant or causing concern.

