### **Enrollment stopping rules**

If the DMC decided that there were a pattern consistent with an important increase in frequency of the occurrence of one or more types of SAEs then a review by the DMC Chair will be requested.

The DMC, upon review of the participant-specific reported SAEs, will: Convene a meeting of the full DMC for the purpose of providing a recommendation to the investigator regarding cessation or continuation of enrollment in the study. Such recommendation will be formally provided within 24 hours of such meeting and will not be influenced by actions or opinion of the any of the investigators; Recommend that enrollment in the study be halted if as many as three (3) participants that received treatment with FMT were reported to experience the same or substantially similar types of SAE and the DMC concluded that such SAEs could be reasonably related to treatment with FMT; Recommend that enrollment in the study be halted if any one participant who received treatment with FMT were reported to experience an SAE that had fatal or life-threatening outcome and the DMC concluded that such SAE could be reasonably related to FMT.

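### As most naturally read, the SAE routing clause sends the DMC only events the investigator rates at least possibly related, which does not fit the enrollment stopping rules

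*Combined protocol and SAP*

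**What the plan says.** Under Trial steering and the data safety and monitoring committee, the protocol says the DMC will "receive (verbatim) each report of a serious adverse event (SAE), with an investigator assessment of causality/attributability of at least possibly related to study". The same sentence goes on to say that "follow-up SAE reports will be promptly forwarded to the Chair", with no relatedness wording of its own. Meetings are periodic and normally fall "after data on the first 20% of participants have been enrolled into a study, and at the conclusion of enrollment". The section does not say which safety data are tabled at them.

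Enrollment stopping rules gives the DMC three tasks. It is to watch for a rise in the frequency of "one or more types of SAEs then a review by the DMC Chair will be requested". It is to recommend a halt if three participants treated with FMT have similar SAEs and "the DMC concluded that such SAEs could be reasonably related to treatment with FMT". It is to recommend a halt after one fatal or life-threatening SAE, again on its own conclusion about relatedness. It acts "upon review of the participant-specific reported SAEs", and its recommendation "will not be influenced by actions or opinion of the any of the investigators".

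Adverse Event Reporting says: "All adverse drug event (ADE) and serious adverse events (SAE) will be tracked". The places named are the study file, REDCap and the ethics board, and all AEs go to the ethics board within 24 hours. The DMC is not named as a recipient.

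**The concern.** The stopping rules assume a committee that can see SAEs and judge for itself whether FMT was responsible. The routing clause, as most naturally read, puts the investigator's judgement ahead of the committee's: an SAE rated unrelated is not sent. A rise in the frequency of a type of SAE cannot be judged reliably from reports already selected on relatedness, and the DMC cannot disagree with a rating on an event it has not received.

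The trial is open-label and no control arm is described. The rating is therefore made with treatment known, and there is no concurrent comparison in which an excess of events first thought unrelated could show up.

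**Working it through.** No alpha, power or sample size figure bears on this point, and the plan states no figure to reproduce. The check sets the sections side by side.

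1. **Two readings of the routing clause.** On the restricted reading, the DMC receives SAE reports rated at least possibly related. On the open reading, it receives every SAE report with a causality rating attached. The open reading leaves the words that fix the rating at possibly related or higher with nothing to do, because an event rated unrelated cannot carry that rating. The restricted reading gives every word a function. The follow-up clause most naturally means follow-up to the reports just described.

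2. **Other routes to the DMC.** Adverse Event Reporting has no attribution filter for the ethics board but does not mention the DMC. The proposed frequency of analyses has a safety and feasibility interim after 15 patients, for the dysbiosis group only, and names no reviewing body. The DMC section does not list what its meetings see. The text available for review lacked a portion at the start and one directly after Enrollment stopping rules, so a route stated there cannot be excluded.

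3. **Restricted supply against each rule.**

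| Rule | Relatedness condition | Fit with restricted supply |
|---|---|---|
| Rise in frequency of SAE types, leading to Chair review | None in the wording | Does not fit: the count is taken on a selected subset |
| Three similar SAEs, leading to a halt recommendation | DMC concludes reasonably related | Partial fit: the screen is lower than the test, but ratings of unrelated are never tested |
| One fatal or life-threatening SAE, leading to a halt recommendation | DMC concludes reasonably related | Same partial fit |

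4. **Count at the stated thresholds, restricted reading.** Reports received = SAEs occurring − SAEs rated unrelated.
   - Three similar SAEs, one rated unrelated: 3 − 1 = 2, below the threshold of 3.
   - One fatal or life-threatening SAE, rated unrelated: 1 − 1 = 0, below the threshold of 1.

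   These counts change a recommendation only if the DMC, had it seen the event, would have concluded that it was related. They show that one unsent report can matter at these thresholds. They do not show how often that would happen.

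5. **What counts as an SAE.** Adverse Event Reporting first defines an SAE as a kind of adverse drug reaction, which implies a causal link. It then treats SAEs attributed to FMT as a subset, and in its expedited-reporting text uses broader wording about untoward occurrences with no causal element. The second and third usages fit a DMC that has to decide relatedness; the first does not.

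**The case against.** The strongest defence is the SAE definition. If an SAE is by definition an adverse drug reaction, the frequency trigger is already confined to events thought to be drug-related, and the routing filter and the trigger largely line up. This stands in part: whether the trigger is unrestricted depends on a definition the protocol does not use consistently. It does not remove the problem. The same section speaks of SAEs attributed to FMT as a subset, and the halting rules would not need a DMC conclusion on relatedness if every SAE were related by definition.

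A reader might infer that the filter disables the halting rules. The documents do not support that. A low investigator screen followed by a stricter DMC judgement is a coherent two-stage process, and "upon review of the participant-specific reported SAEs" may simply refer back to the screened reports. What remains is the narrower gap: an event rated unrelated that the DMC would have judged otherwise.

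A reader might also infer a breach of the clause that the recommendation "will not be influenced by actions or opinion of the any of the investigators". That clause governs the recommendation made after a DMC meeting, not the supply of reports. The filter sits awkwardly with its purpose but does not contradict its words.

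Nor does the spacing of the two named meetings measure the problem: it would be the same with no filter. Meetings are only normally at those points, event-driven meetings are allowed, and a fuller SAE review at a meeting is possible though not stated. Event-driven meetings, however, depend on reported SAEs, and a review at the end of enrollment comes too late to halt it.

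Finally, the open reading may be what the sponsor intended. If so, the sentence still needs repair, because staff must apply it as written.

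**Conclusion.** The point holds as a drafting defect with a safety consequence. As most naturally read, the routing clause withholds from the DMC any SAE the investigator rates unrelated; no available section supplies those events by another route; and this does not fit the stopping rules. The inconsistent SAE wording in Adverse Event Reporting adds to the ambiguity.

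The main exposure is the frequency trigger, whose stated consequence is a Chair review and not a halt. The halting rules are exposed only where the DMC would have overturned a rating of unrelated. The size cannot be computed: the documents give neither an SAE rate nor a rate of misattribution, and any probability would rest on assumed values for both. The conclusion assumes the restricted reading and that the missing portions of the text contain no other route. The correction is worth making because it is cheap and settles the ambiguity whichever reading was intended.

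**What to change.** Reconcile the three sections by replacing the SAE clause in Trial steering and the data safety and monitoring committee with:

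> Every serious adverse event (any untoward medical event that meets a seriousness criterion, regardless of causality) in a participant who received FMT, initial and follow-up, is promptly forwarded to the DMC Chair with the investigator's causality rating attached. A cumulative SAE listing is provided at each DMC meeting.

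The words on causality are needed: without them, the adverse-drug-reaction definition could bring the filter back. The thresholds in Enrollment stopping rules and the expedited regulatory reporting in Adverse Event Reporting stay unchanged. Limiting the frequency trigger to the reports the DMC already receives would also make the text consistent, but it would leave the committee with less to judge.

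The cost is a few extra reports to the Chair, whose number cannot be derived from the documents, and one listing per meeting among 70 planned participants (50 dysbiosis + 20 ARO). SAEs are already tracked in REDCap, so no new data collection is needed.

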### **Enrollment stopping rules**

If the DMC decided that there were a pattern consistent with an important increase in frequency of the occurrence of one or more types of SAEs then a review by the DMC Chair will be requested.

The DMC, upon review of the participant-specific reported SAEs, will: Convene a meeting of the full DMC for the purpose of providing a recommendation to the investigator regarding cessation or continuation of enrollment in the study. Such recommendation will be formally provided within 24 hours of such meeting and will not be influenced by actions or opinion of the any of the investigators; Recommend that enrollment in the study be halted if as many as three (3) participants that received treatment with FMT were reported to experience the same or substantially similar types of SAE and the DMC concluded that such SAEs could be reasonably related to treatment with FMT; Recommend that enrollment in the study be halted if any one participant who received treatment with FMT were reported to experience an SAE that had fatal or life-threatening outcome and the DMC concluded that such SAE could be reasonably related to FMT.

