### **The planned trial interventions**

#### **Recruitment**

The research coordinator will be responsible for coordinating the recruitment, screening of potential participants using the inclusion/exclusion criteria and reviewing with the PI. The PI will make the final determination of a potential participants' eligibility. Fifty participants with chronic GI dysbiosis will be recruited. Twenty patients with confirmed ARO will be recruited to take part in this study; the ARO study results will be used to determine the feasibility of further study.

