#### **ARO Participants**

Following informed consent and prior to receiving FMT, enrolled ARO participants will have their blood collected for Hepatitis BsAg, Hepatitis C Ab, HIV, Syphilis serologies. Blood is collected for these pathogens to determine their serostatus at the time of study enrollment. Participants are advised through the study consent that if their blood tests positive for any of these diseases, the researchers are required to notify the public health department and that the public health department may contact them.

At baseline, ARO participants will have medical history, physical exam done by the physician-researcher, and information on concomitant medications will be collected. The participants will receive a total of two lyophilized FMT (LYO-FMT) or frozen FMT enemas using stool samples collected from healthy, screened donor(s); the participant will receive the first FMT treatment week 1 and a second FMT will be administered within three weeks of first treatment. Participant's stool will be retested one week, one month and 3 months following the second FMT to determine whether the ARO has been eradicated.

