## GI Dysbiosis Participants

Following informed consent and pre-transplant, enrolled participants will have their blood collected for Hepatitis BsAg, Hepatitis C Ab, HIV, Syphilis serologies unless these serologies were performed within 3 months of enrollment. Blood is collected for these pathogens to determine their serostatus at the time of study enrollment and prior to receiving FMT.

All participants will be assessed at day 1 by the physician-investigator. A medical history and physical examination will be performed. In addition, optional blood and stool samples may be collected from IBD/IBS participants who consented for these samples prior to the FMT and at weeks 4, 12 and 6 months from FMT.

The participants will receive lyophilized FMT (LYO-FMT) or frozen FMT enemas using stool collected from healthy, screened donor(s). Participants will receive FMT treatment via retention enema(s) twice weekly for 4 weeks. If there is symptom improvement after 4 weeks of treatment, then the participants will receive FMT treatment once weekly for 4 additional weeks. If the participant does not experience symptom improvement after the initial 4 weeks of treatment, the physician-investigator will discuss options with the participant and a mutual decision will be reached to pursue an additional 4 weeks of FMT treatment or withdraw from the study and pursue usual care. When continued improvement is seen then the participants will receive FMT maintenance; the frequency of FMT treatment is participant dependent and is at the discretion of the physician-investigator and is based upon clinical exam and symptomatic improvement. If no improvement is seen after the 8th FMT, then the participant will be withdrawn from the study and s/he reverts to usual care for his/her condition. Participants can opt to receive maintenance FMT in the clinic or be trained by study staff for home administration.

At the time of each study visit and follow up, participants will be assessed for clinical response, including bowel movements and adverse reactions. Any participant who reports worsening symptoms or AE/SAE will return to the clinic for assessment by the physician investigator. At that time, the participant will undergo a physical exam. Additional tests may be ordered (i.e. blood work) at the discretion of the treating physician investigator.

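### The DMC's serious-event rules concern enrolment only, so the available text sets no recommendation on FMT dosing for participants already enrolled

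*Combined protocol and SAP*

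**What the plan says.** The protocol and SAP are one combined document. Its Enrollment stopping rules section says that, after reviewing reported SAEs, the DMC convenes in full "for the purpose of providing a recommendation to the investigator regarding cessation or continuation of enrollment in the study". Two triggers follow, and both require the DMC to conclude that the events could reasonably be related to FMT:

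- **Cluster:** "Recommend that enrollment in the study be halted if as many as three (3) participants that received treatment with FMT" have the same or a closely similar type of SAE.
- **Single event:** "Recommend that enrollment in the study be halted if any one participant who received treatment with FMT" has an SAE that is fatal or life-threatening.

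In both cases the recommendation is to halt enrolment.

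On the committee's wider role, the Trial steering section says that "this committee will continue to serve to oversee until the completion of the trial".

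On dosing, GI Dysbiosis Participants states: "Participants will receive FMT treatment via retention enema(s) twice weekly for 4 weeks". Those who improve then have weekly FMT for four more weeks. Those who do not improve either leave the study or, by agreement with the physician-investigator, continue for four more weeks. Continued improvement leads to maintenance at a frequency the physician-investigator decides. After month 6, optional maintenance ranges from one FMT every two weeks to one every six months. No end is given, and trained participants or household members may store and give it at home. For the ARO group, ARO Participants states that "a second FMT will be administered within three weeks of first treatment".

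**The concern.** In a single-dose trial, halting enrolment comes close to halting exposure. Here it does not, because each enrolled person has further doses scheduled. If the DMC concludes that a death, a life-threatening event or a cluster of SAEs could reasonably be due to FMT, the people most immediately exposed to that risk are those still being dosed. The written rules give a definite answer for people not yet enrolled and none for these participants.

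The hazard is one the protocol itself recognises. FMT Side Effects reports transmission of a multi-drug resistant organism to FMT recipients from a donor whose stool had not been screened for it, and accepts that a small risk may remain despite screening. A product-related event of that kind bears on everyone receiving FMT, not only on the next person enrolled.

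**Working it through.** The plan gives no figure to reproduce on this point. The check sets the rule beside the dosing schedule and then asks whether another section supplies the missing action.

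**1. What the rules act on.** The stated meeting purpose and both triggers name enrolment. None of the three mentions giving, pausing or stopping FMT.

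**2. Dosing after enrolment** (GI Dysbiosis Participants; ARO Participants).

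| Stage | Arithmetic | FMTs |
|---|---|---|
| Dysbiosis, weeks 1–4 | 2 per week × 4 weeks | 8 |
| Dysbiosis improver, weeks 5–8 | 1 per week × 4 weeks | 4 |
| Improver, total by week 8 | 8 + 4 | 12 |
| Maintenance to month 6 | frequency left to the physician-investigator | not stated |
| Optional maintenance after month 6, per 26 weeks | 26/26 to 26/2 | 1 to 13 |
| ARO participant | first FMT, then a second within three weeks | 2 |

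An enrolment halt by itself stops none of these doses.

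**3. After enrolment closes.** Consider whoever is enrolled last. As scheduled, a dysbiosis participant still has 8 FMTs to come and an ARO participant 2. Earlier improvers may be on maintenance. If a trigger is met then, the defined recommendation is to halt enrolment that has already ended. The two halting rules have no operative effect, although dosing can continue.

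**4. Whether another section defines a dosing action.**

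- *Enrollment stopping rules, opening paragraph:* a pattern of increased SAEs leads to a review by the DMC Chair. No action on dosing follows.
- *Trial steering:* oversight to completion, with SAE reports judged at least possibly related going to the committee. No action on dosing.
- *The proposed frequency of analyses:* an interim look at safety and feasibility after 15 patients, for the dysbiosis group. No stopping action is stated.
- *Adverse Event Reporting:* ethics board reporting within 24 hours of the investigator's awareness, and expedited reporting of qualifying SAEs to Health Canada. No dosing hold.
- *GI Dysbiosis Participants:* someone who reports worsening or an adverse event is assessed in clinic. Nothing is said about the dosing of others, and the withdrawals defined there are for lack of improvement.
- *Home-maintenance conditions (same section):* six conditions, none of them a safety hold or an instruction about stored FMT.
- *FMT Side Effects:* stool from a donor with abnormal results is kept out of processing. Product already processed or delivered is not mentioned.

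No available section supplies the missing action. Part of the document after the stopping rules was not available for this review. The contents list shows Trial Organization as the next section, but its content could not be checked.

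**The case against.** The strongest reply is that silence is not a prohibition. Nothing bars the DMC from advising on dosing. It serves to the end of the trial, and its SAE-triggered meeting has no end date. The trial is open-label, the physician-investigator sets maintenance frequency, and reports reach the ethics board and, where they qualify, Health Canada. Any of these parties could stop dosing. The protocol also says that UC responders in an earlier trial needed ongoing maintenance to stay symptom-free, so leaving suspension to case-by-case judgement can be defended.

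Most of this stands, and it rules out several stronger readings:

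- A reader might infer that enrolled participants would go on receiving FMT after a related death. No section says so. The text simply does not say what should happen.
- A reader might infer that the DMC has no role after enrolment closes. It can still meet and advise. Only the two halting rules lose their effect.
- A reader might take everyone enrolled at the time of a trigger as the number at risk. That count applies to any enrolment rule and measures no risk. ARO dosing is short, and non-improvers may have left.
- A reader might try to calculate how much FMT a household holds when a trigger occurs. The three-week period in the home-maintenance conditions can be read as notice for a request or as lead time for delivery, and no quantity is given.

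The reply does not dispose of the narrower point. The plan pre-specifies an independent recommendation for enrolment, to be free of investigator influence, and leaves the more urgent question of dosing without one.

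**Conclusion.** The concern holds in a limited form. The meeting's stated purpose and both SAE triggers are directed at enrolment, while exposure continues through repeated and open-ended dosing. The available text pre-specifies no dosing recommendation for enrolled participants when a trigger is met, and the halting rules do nothing once enrolment closes. This is more than missing detail, because a stated safety rule is aimed at the wrong target.

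Its scale is the scheduled exposure that the rules do not reach: 8 to 12 FMTs in the first eight weeks for dysbiosis participants who leave after week 4 or improve, 1 to 13 per 26 weeks for those in optional maintenance after month 6, and up to 2 for ARO participants. Non-improvers who continue past week 4 do so at an unstated frequency. The documents give no SAE rate, so the probability of a trigger is not estimated. Other safeguards reduce the gap without closing it. The conclusion assumes that the unavailable text contains no dosing rule. The change is worth making mainly because it is cheap.

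**What to change.** Amend Enrollment stopping rules, and its heading, so that they cover dosing as well as enrolment. When either trigger is met, at any time until the last study FMT has been given:

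1. The DMC recommends a temporary hold on all study FMT, in clinic and at home, together with the enrolment halt.
2. Participants on home maintenance are told at once not to use stored FMT.
3. The full DMC then recommends resumption, modification or permanent stop.

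The hold should be the default. Asking the DMC only to consider whether to suspend would add little to the discretion it already has.

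The cost is a few sentences, with no change to sample size, visit schedule or analysis. The downside is a temporary interruption for responders who depend on maintenance, a real cost given the earlier UC experience. The existing 24-hour clause does not by itself bound that pause, because it runs from the DMC meeting and no deadline is set for convening one. If the sponsor wants the pause bounded, it should also state a time limit for holding the meeting.
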